7.3 Adverse Events and Serious Adverse Events

Definitions for Adverse Events (AEs)

An **Adverse Event (AE)** is any untoward medical occurrence, including any abnormal sign, symptom, or disease *temporally* associated with study participation, whether or not considered related to participation in the research.

- An AE is deemed to be associated with the use of the study device if there is "a reasonable possibility that the experience may have been caused by the device."
- Chronic problems which are unchanged from baseline are not considered AEs. However, worsening of an ongoing condition would be considered an AE.

A **Serious Adverse Event (SAE)** is an adverse event that

- results in death

- is life-threatening, or places the participant at immediate risk of death from the event as it occurred
- requires or prolongs hospitalization
- leads to persistent or significant disability or incapacity
- is a seizure (Note: intervention-specific SAE definition)
- Is another condition which investigators judge to represent significant hazards.

An **Unanticipated Adverse Device Effect (UADE)** is an SAE caused by or associated with a device, if that effect, problem, or death was not previously identified in nature, severity, or degree of incidence, or any other unanticipated serious problem associated with a device that relates to the rights, safety, or welfare of patients.

Time span of collecting AEs and SAEs

Collection of all adverse events will begin at the time the participant signs the informed consent form and will continue throughout the 6-month post-intervention follow-up phase:

- At the Baseline visit, the participant and study partner (SP) will be asked about changes in medications, any other health or behavior changes, and any medical care received since the Screening visit;
- At each Intervention session, the participant will be asked about any side effects experienced. At each morning Intervention session, the participant will additionally be asked about any changes in medications, any other health or behavior changes, and any medical care received;
- At the Immediate Post-Intervention Follow-up visit, the participant will be asked about any side effects experienced since last seen, and any changes in medications, any or other health or behavior changes since the previous visit or phone follow-up, and any medical care received;

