- At the 3- and 6-Month Follow-up visits, the participant will be asked about any changes in medications, medical care received, or other health or behavior changes since the previous visit or phone follow-up.

In summary, study staff will screen for new AEs/SAEs and review any unresolved AEs/SAEs at each encounter with the participant.

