7.4 Reporting Procedures

Time lines for reporting AEs and SAEs

The PI and research team will notify the DSMB and the NIA Program Official of all SAEs (regardless of intervention vs. follow-up phase) by group email within 24 hours of study staff's knowledge of the event.

- The emailed, expedited report will be followed by a detailed, written initial SAE report as soon as possible.
- The PI is responsible for verifying that the report has been submitted and that the DSMB Chair and NIA Program Official acknowledge receipt.

The PI and research team will report SAEs to the local IRB per Stanford University's HRPP Policy Guidance "Events and Information that Require Prompt Reporting to the IRB" GUI-P13 1/3 (see Appendix X).

All adverse events will be reported annually or more often to the DSMB, Stanford IRB, and NIA staff.

- The study's Data Manager will generate tabulations of all AEs (including SAEs and non-serious AEs) and present a summary of these to the DSMB and NIA staff on a schedule set by the DSMB.
- Aggregate summaries of SAEs and non-serious AEs will also be reported annually to the Stanford IRB.

Procedures and forms for recording AEs

Any new condition, recurrence of a previously resolved condition, or worsening of a pre-existing condition will be reported as an AE. (The Screening Visit Medical History Form provides a list of all pre-existing conditions and whether each condition is resolved or ongoing.)

All adverse events (including adverse device effects) will be recorded on the AE report form (based on NIH Template AE form 9a) and, if severe, on the SAE form (based on NIH Template SAE form 9b). Both SAEs and UADEs will be recorded using SAE form 9b. All adverse events will be assessed as "Not related," "Possibly related," or "Definitely Related" to the intervention or to other study procedures.

Decisions regarding AE relatedness and severity

The Study Physician will be responsible for decisions regarding relatedness and severity.

Assessment of study relatedness. Relatedness involves an assessment of the degree of causality between the study intervention and the event. Relatedness can be assessed by considering the following criteria:

- Previously reported with this treatment,
- Occurred after treatment began,
- Improved when treatment is withdrawn or a specific antagonist administered,
- Reappearance upon re-challenge,
- No alternative causes for the reaction,
- Increased severity when dose increased or lessened when dose decreased,

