- Patient previously had similar reaction when exposed to the treatment, and
- Reaction confirmed by objective evidence.

Study-relatedness criteria.

- All adverse events or effects with a clear causal relationship to the intervention or to the procedures involved in the research should be considered "**Definitely related**".
- All adverse events or effects with a possible causal relationship to the intervention or to the procedures involved in the research should be considered "**Possibly related**".
- In general, if event is determined to be caused solely by an underlying disease, disorder, or condition of the subject, or due to other circumstances unrelated to either the research or any underlying disease, disorder, or condition of the subject, it would be considered "**Unrelated**" to participation in the research.

Study Staff Responsibilities

- During the pre- and post-intervention phase of the study, the Study Coordinator will be responsible for collection of initial AEs, follow-up of AEs (see Section 7.5) and completion of AE forms.
- The TMS Operator will be responsible for initial AE collection, follow-up, and form completion during the intervention phase.
- The Study Physician will be responsible for reviewing all AEs and for making decisions regarding relatedness and severity.
- The PI will be responsible for reviewing the AE forms for completeness and accuracy, for monitoring the AE data to avoid double capture of AEs, and for monitoring charts and CRFs for documentation of the physician's review of AEs.

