7.5 Follow-up of Adverse Events

All AEs will be followed until resolution, or until the patient's participation in the study ends. For a participant who ends study participation prior to the 3-month follow-up visit (Visit 14), unresolved SAEs/UADEs will be monitored and reported for 30 days after the date the participant was last-seen.

An AE will be considered “**resolved**” when one of the following criteria are met:

- Health has returned to baseline status or applicable variables have returned to normal.
- The event has stabilized and the study staff expect no further improvement or worsening of the event.

If the Adverse Event does not resolve and it has been determined that the condition is stable or chronic, then the event can be considered “resolved with sequelae”.

The study staff are also responsible for following up on AE/SAE information that was initially incomplete. Whenever new information about an SAE is obtained, the staff is responsible for reporting the follow-up information as soon as it becomes available.

Examples of incomplete AE/SAE information that may require follow up:

- An event for which complete information was not available at the time of reporting to the DSMB or NIA Program Official.
- Update or new information related to an event that was previously reported (e.g. receipt of hospitalization records, clarity from study participant on event details).

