8 INTERVENTION DISCONTINUATION

8.1 Permanent discontinuation of the study intervention

The study intervention will be discontinued if:

- A participant has a seizure;
- There are signs or reports of inability to tolerate the intervention. Specifically, the participant will no longer continue with the intervention if the participant either reports or indicates upon questioning that a side effect (such as a headache) is not well tolerated despite self-treatment (e.g. severe in intensity and persists beyond the first week of treatment), or if the study physician feels it is in the participant’s best interest to discontinue with the intervention.
- Or, any other health or safety concern that contraindicates continuation, based on the judgment of the study physician.

Continued follow-up will occur in each of these cases. The participant will be closely monitored and treated for any medical or psychological consequences. The Study Coordinator will be responsible for phone follow-ups to check on the participant’s well-being and to collect follow-up AE information.

Such participants will be encouraged to return for all three post-intervention follow-up evaluations (Visits 13, 14, and 15). Except for the MRI scan (Visit 13), all other outcome

measures, safety assessments, and AE information would be collected at the three follow-up visits.

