To explore the extent to which one treatment is superior over another as a function of a moderator variable, we will fit regression models with interactions between the treatment group variable and a selected moderator variable, yielding estimates of the regression line for each group. In addition to reporting the magnitude of the interaction as a p value, we will obtain predicted values of the regression lines corresponding to each group. (From these, we can estimate the superiority of one treatment over another as a function of the moderator; confidence intervals and p-values can be readily reported). As these are exploratory analyses, we would analyze individual moderators separately to avoid over-fitting the models.

Based on limited data from previous TMS studies, the following classes of moderators are most likely to account for heterogeneity of response to rTMS in patients with MCI:

- Profiles of baseline cognitive deficits, as defined by CVLT-II clustering and delayed recall scores;
- Brain endophenotypes, as defined by a baseline functional connectivity metric for the Language, Central Executive, and Default-mode Networks;
- BDNF met carrier status (in other clinical populations, val/val genotype has predicted a better response to rTMS (Chang et al., 2014; Cheeran et al., 2008)).

In addition, gender and racial/ethnic categorical variables will be examined to gauge the magnitude of any potential differences in response to rTMS in patients with MCI.

Descriptive analyses of safety and tolerability

Adverse events will be coded according to established Medical Dictionary for Regulatory Activities (MedDRA) terms and summarized by MedDRA System Organ Class and Preferred Term. In most cases, aggregate safety and tolerability data (see Section 7.2) will be summarized with descriptive statistics (counts, percentages, mean and standard deviation) for all participants, by treatment group and by study phase (i.e., intervention and follow-up). Summaries will indicate whether events were determined to be related to the study device and whether the AE led to treatment discontinuation. Inferential comparisons may include t-tests or chi-square tests as appropriate. The time course of incidence of common treatment-related adverse effects will be examined to characterize the extent to which participants accommodated to the treatment.

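### Incidence of adverse effects over time can fall without any accommodation to rTMS; per-session symptom prevalence would measure it more directly

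*Combined protocol and SAP*

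**What the plan says.** The descriptive safety and tolerability part of Section 9.5.2 states: "The time course of incidence of common treatment-related adverse effects will be examined to characterize the extent to which participants accommodated to the treatment". It does not define incidence, the time intervals, the counting unit or the denominator for this analysis.

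The following provisions decide what that incidence would contain:

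- **What counts as an AE (Section 7.4):** "Any new condition, recurrence of a previously resolved condition, or worsening of a pre-existing condition will be reported as an AE". The same section makes the PI responsible "for monitoring the AE data to avoid double capture of AEs".
- **When an AE is closed (Section 7.5):** one of the criteria for resolution is "The event has stabilized and the study staff expect no further improvement or worsening of the event".
- **Who leaves treatment (Section 8.1):** "the participant will no longer continue with the intervention if the participant either reports or indicates upon questioning that a side effect" is poorly tolerated despite self-treatment. The example given is a side effect that is "severe in intensity and persists beyond the first week of treatment".
- **What is elicited (Section 7.3):** "At each Intervention session, the participant will be asked about any side effects experienced". Staff also "review any unresolved AEs/SAEs at each encounter with the participant".

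**The concern.** Accommodation is a change in symptom level within people who go on receiving stimulation. The protocol itself treats it that way: Section 5.2 expects tolerance to develop over the first 5 to 10 sessions, and Section 7.1.4 expects reported discomfort to lessen in later sessions. A count of new events measures something else, and two features of the plan can make it fall for other reasons.

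First, a headache that starts at Session 1 and stays the same is neither new, recurrent nor worse at Sessions 2 to 20. It adds one event at the start and none later, although the participant has not improved. Second, a participant who stops because of a side effect can add no later on-treatment events.

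Both push the curve in the direction the protocol already expects. Tolerability is a stated assessment (Section 7.2) and the study is meant to inform later trials, so an over-favourable account of accommodation could be carried forward. Comparing arms would not necessarily remove the problem, since active and sham may differ in persistent symptoms and in stopping for intolerance.

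**Working it through.** The plan gives no figure for this analysis, so there is none to reproduce. The check asks what the planned measure would show if nobody accommodated.

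**Inputs from the documents.** Headache in up to 30% of patients and site discomfort in 15% (Section 2.2, summary of risks); 20 sessions (Section 5.2); attrition of 0% so far in a TBI trial at the same site and 6% from all causes in an earlier MCI trial (Section 9.2).

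**Assumptions.** In steps 1 and 3, the documents' patient percentages are used as the share affected in each half of the course, with first onset in Sessions 1-10 and no improvement in anyone. The share q of affected participants whose symptom persists between sessions is unknown, so the full range is shown.

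**Step 1: continuing symptoms.** Participants with a new event in Sessions 11-20, per 100, number 30 × (1 − q). The number actually symptomatic is 30 throughout.

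| q | New event, Sessions 1-10 | New event, Sessions 11-20 | Symptomatic in both halves |
|---|---|---|---|
| 0 | 30 | 30 | 30 |
| 0.25 | 30 | 22.5 | 30 |
| 0.50 | 30 | 15 | 30 |
| 1 | 30 | 0 | 30 |

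**Step 2: counting unit and denominator.** Now take 30% as a constant per-session probability of headache.

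- If every recurrence counts as a new AE, each half has 10 × 0.30 = 3.0 AEs per participant. The line is flat.
- If only first occurrences count, Sessions 1-10 have 1 − 0.7^10 = 97.2 per 100 and Sessions 11-20 have 0.7^10 − 0.7^20 = 2.7 per 100.

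The same experience gives a flat line or a near-total fall, depending on a rule that 9.5.2 does not state.

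The denominator matters too. Suppose instead that headache has a constant onset hazard, never resolves, and reaches 30% cumulatively over 20 sessions. The hazard is h = 1 − 0.7^(1/20) = 0.0177. New onsets per 100 enrolled go from 1.77 at Session 1 to 1.77 × (1 − 0.0177)^19 = 1.26 at Session 20. Among those still symptom-free the rate is flat.

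**Step 3: loss of non-tolerators.** If a fraction d of participants, all symptomatic, stops, the symptomatic proportion among those still treated is (p − d)/(1 − d).

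| d | Headache, p = 0.30 | Site discomfort, p = 0.15 |
|---|---|---|
| 0 | 30% | 15% |
| 0.03 | 0.27/0.97 = 27.8% | 0.12/0.97 = 12.4% |
| 0.06 | 0.24/0.94 = 25.5% | 0.09/0.94 = 9.6% |

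The last row is an extreme, because it assigns all-cause attrition entirely to participants with that one symptom. It also shows that a per-session proportion among those treated is not fully protected unless stoppers are displayed beside it.

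**The case against.** A reader might infer that incidence must fall even when nobody accommodates. The documents do not support that. Section 7.4 counts a recurrence after resolution as an AE, and Section 7.3 asks about side effects at every session. A headache that clears and returns therefore gives flat incidence (q = 0 in step 1, and the first case in step 2). The documents do not say how repeated session-related symptoms are counted, so which case applies cannot be settled. The double-capture duty may mean no more than removing duplicate records of one event.

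A reader might also infer that stoppers stay in the denominator and are classed as accommodated. The reference in 9.5.2 to all participants belongs to the general AE summaries, not to the time-course sentence, and no participant-level classification is planned. Stoppers are not hidden either: 9.5.2 will indicate whether an AE led to discontinuation, and Section 7.2 counts dropouts due to AEs. The example in Section 8.1 concerns severe side effects, whereas Section 2.2 expects mild to moderate headaches, so depletion may well be small.

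All of this stands and limits the point to what can happen. It does not rescue the measure: nothing in 9.5.2 prevents either artefact, and discontinuations reported in another table do not correct a time-course display that omits them.

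**Conclusion.** The concern holds in a limited form: the time course of incidence can fall without accommodation, so it is not a sound basis for describing accommodation. At 30% affected, the fall from continuing symptoms ranges from none (all clear and recur) to 30 down to 0 new events per 100 (all persist). The persistent share is not given in the documents and is the main uncertainty.

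Depletion adds nil at 0% attrition. At the 6% extreme it lowers headache by 4.5 percentage points (30% to 25.5%) and site discomfort by 5.4 (15% to 9.6%) among those still treated. Because the step 1 and step 3 figures use a percentage of patients as a constant level over the course, they illustrate the mechanism and do not predict the result.

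Severity is minor. This is one sentence in a descriptive tolerability analysis with no decision rule attached, and the primary test on the CVLT-II is unaffected.

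**What to change.** In 9.5.2, base accommodation on per-session prevalence. For each common side effect and session, by arm, report the number of participants reporting the symptom (with severity where recorded) divided by the number who received that session. In the same display, show participants who stopped the intervention because of that side effect as a separate not-accommodated category. Keep new-onset incidence as a separate AE table with its counting unit and denominator stated.

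Take the data mainly from the side-effect question asked at every session (Section 7.3) and the intervention log (Section 6.2.3). AE recovery dates should not be the main source: Section 7.5 lets a merely stabilized event be closed as resolved, so an unchanged symptom could be dropped from the count. The forms are not in the documents, so the team should confirm that the per-session answer is stored for each common symptom and not only used as a prompt.

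Prevalence can still change for reasons other than accommodation, such as self-treatment (Section 7.1.4) and the optional intensity ramp in the first two sessions (Section 5.2). The text should say so.

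The cost is one or two sentences and slightly more programming, with no added visits. Accommodation may look less favourable than under the present wording.

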10 DATA COLLECTION AND QUALITY ASSURANCE

10.1 Data Management

In this single-site study, the PI and study team are responsible for all data collection and management. The Database Manager will monitor all data entered into the database by the Study Coordinator. The PI will review data on an ongoing basis at regularly scheduled staff meetings. A formal review of the accumulating data and any data integrity issues will be conducted at a meeting of the PI and the Data Manager every 3 months during the active data collection period.

Information about adverse events will be collected at each visit. Any potentially serious problem will be brought immediately to the attention of the PI and the Study Physician.

Biomarker/genetic information will be stored in a separate password-protected file, in a separate database, which can only be accessed by the Study Data Manager and MIRECC Senior Data Manager. Only the Data Managers can match genetic information with the participant ID (PID); the Data Managers are blinded as to which PID is associated with which study participant. The genetic data will only be used for analysis of data conducted by the Data Manager.

The Participant ID (PID) will be recorded on all data collection forms and entered into encrypted, password-protected databases located on physically secure VA servers behind a firewall.

10.2 Data Collection Forms

Data collection forms include:

- Original copyrighted test forms (e.g. CVLT-II);
- Standard questionnaires (e.g. ECog form and GDS like those used in the Alzheimer's Disease Neuroimaging Initiative [ADNI]);
- Case report forms adapted from the NIH Clinical Trial Toolkit (e.g. Participant Demographic form, Enrollment & Randomization form, Vital Signs form, and Adverse Event Forms).
- Forms developed specifically for this study, many of which were adapted from VA CSP #556 (e.g. Inclusion-Exclusion Form, and rTMS Intervention Log sheet).

No data collection forms will show an individual participant's identifiers, such as name or initials. For additional steps taken to maintain participants' confidentiality, please see Section 11.3. For information regarding which members of the study team will fill out the about forms, please see Section 6.2.

10.3 Quality Assurance

10.3.1 Training

General Training. All staff will have completed all VA- and Stanford-required online training in Human Subjects, Good Clinical Practice (GCP), Privacy, and HIPAA before engaging in any study-related activities. Each member of the study staff will have completed training specific to their scope of practice and specific to their roles before performing study procedures. These types of training include:

TMS Training. Didactic and practical hands-on training will be provided onsite to the study staff at VA-Palo using the training model of the VA-funded, Mental Illness Research, Education, and Clinical Center (MIRECC)-led "TMS Clinical Roll-out" training program. The trainers will be rTMS-certified physicians and nurses. The didactic materials include the MagVita TMS Therapy User Guide for use with MagVenture MagPro devices, software version 7.1.

Study Staff TMS Safety training. Multiple study personnel, including the Study Coordinator and TMS Operator, will be trained comprehensively in TMS safety procedures, including: pre-session safety screening, solicitation and recognition of AEs, and training as first responders per the seizure protocol. Knowledge will be demonstrated by taking a written examination that includes questions on what to do if there is a TMS-induced seizure. Annual drills simulating a TMS emergency will be conducted to maintain staff preparedness.

TMS Operator training. The TMS Operator will be trained to reach proficiency in all aspects of the rTMS intervention procedure, including: device operation, motor thresholding, coil placement for cortical targeting, and delivery of rTMS. Proficiency will be demonstrated by both a written test and by observation-based testing of all aspects of the rTMS intervention procedure. Once the TMS Operator is certified as proficient by the trainers, the TMS Operator's research scope of practice will allow the operator to independently administer rTMS under the supervision of an rTMS-certified physician. This aspect of training is the "Core" component of TMS Certification. Following completion of the Core training, the TMS Operator will be trained to proficiency in the specific stimulation protocol of this study, and certified by the PI.

Assessments Training. The Study Coordinator will be trained in the administration and scoring of the behavioral assessments by the PI. Training will take place in three phases: self-study of the test manuals; practice in administering and scoring the assessments with a trained study coordinator (e.g. the ADNI 3 coordinator), and finally observation by PI to check for adherence to the test manuals. The PI and other staff at the study site who will provide training are experienced in administering these same assessments.

Training of Specific Assessments: CDR. The CDR rater in this study will be another researcher at the study site, so that the CDR—which is part of the screening visit diagnostic evaluation—will be collected independently of the outcome measures. The CDR rater will be certified through Washington University. If the rater has never been CDR certified, full certification will be required. The training includes nine (9) reliability tapes. The ratings/scores are compared to the Gold Standard and, if the rater passes, Washington University will issue a certificate. CDR Certification and Refresher Course can be found online at url: <http://alzheimer.wustl.edu/cdr/application/step1.htm>

Experienced MIRECC personnel associated with the Study Protocol. The following long-time study staff have worked on NIH- and VA-funded protocols that involve similar populations, assessments, biomarkers, and/or interventions (e.g. rTMS clinical trials, older adults, and cognitive outcomes):

[name], Database Manager and SAS Programmer (15% FTE). [name] is presently studying for a Master's in Statistics and has used SAS professionally for over 9 years. She and the PI have worked together 6+ years on cognitive and MRI datasets. She has performed complex analyses, including multiple linear regression modeling and mixed-effects growth curve modeling under the supervision of [name].

She has substantial experience in database management, gained under the direction of [name], the MIRECC Senior Data Manager. [name] will perform randomization of the subjects to treatment arms, to ensure that all other research staff are blinded. [name] will be responsible for setting up REDCap study database for the Study Coordinator to enter screening and other behavioral data. She will also be responsible for dataset merges in SAS and coding the data analyses and models involving the primary and secondary outcome measures.

[name], Laboratory Technician (effort as needed). [name] and the PI have worked together 10 years. [name], who has Bachelor's Degree from UC Davis, has over 10 years of laboratory experience. She has performed complex protocols, including DNA extraction, genotyping assays, microarray genotyping, sequencing, and measurements of gene expression both genome-wide and targeted. She consistently meets a high level of reproducibility, as demonstrated by implementing robust procedures and protocols that resulted in multiple publications over the past decade. Quality control measures of her work have consistently shown that her results are reliable. [name] will be responsible for DNA extraction and tissue banking, and for performing the laboratory protocols for determining BDNF, COMT, and APOE genotypes that will be used in the data analyses relevant to heterogeneity of response to rTMS.

New Staff. Any new staff who join the project will undergo all required training before beginning work on the project, and will be carefully trained on all necessary aspects of the protocol by rTMS-certified physicians, nurses, and the PI.

